## Endpoints for Patient Reported Outcomes

These will be reported in a separate paper. Health-related quality of life (HRQoL) (Questionnaires) correlated to diarrhoea defined by the Hjortswang criteria

- The change in Health-related quality of life (HRQoL) in the primary endpoint population by
  - the Short Form 36 version 2 (SF36v2) items (colesevelam vs. placebo)
    - Physical component score and Mental component score
  - Each of the 4 items in the SHS
- Correlation between HRQoL and Bristol stool scale diarrhoea.
- Correlation between HRQoL and stool number per week.
- Correlation between changes in HRQoL and primary endpoint
- Description of sexual dysfunction with HRQoL in the population
- Six-month follow up on HRQoL

## Power calculation

Based on the primary endpoint we assume

- a remission rate of 67% for colesevelam and 27% for placebo (36, 38).
- two-sided  $\alpha = 0.05$ , and  $\beta = 0.20$  (ie. 80% power); and 1:1 allocation.

Thus, we need 23 subjects with BAD in each arm (G.Power 3.1: z-test of two independent proportions).

As we include all patients with diarrhoea regardless of aetiology, the fraction or prevalence of BAD amongst these eligible patients is crucial. Of 71 subjects in our VABAD study, 59 patients had diarrhoea by Hjortswang criteria and deemed by  $C4 \geq 46$  ng/mL, 16 of the 59 had BAD (27%). In comparison with SeHCAT, Borghede et al. found that 41% of patients referred for SeHCAT had primary BAD defined with SeHCAT (44).

Thus to include 2 x 23 patients with BAD defined with  $C4 > 46$  ng/mL, we need

$$\frac{2 \times 23 \text{ BAD subjects}}{27\% \text{ BAD subjects among patients with diarrhoea}} = 170 \text{ patients with diarrhoea.}$$

## Methods

### Bristol stool form scale

Bristol stool scale classifies stool from hard lumps (1 on the scale) to watery (7 on the scale). A one-week stool diary is usually collected in clinical trials (45, 46). Time and form of stools are noted and further information on pain, urge and incontinence can be obtained. In patients undergoing diagnostic workup for diarrhoea, those with an organic cause of diarrhoea more often have  $\geq 3$  stools per day and watery stool consistency (47) compared with functional diarrhoea.

### Response criteria in chronic watery diarrhoea – Hjortswangs criteria

Hjortswang et al. have validated that disease activity defined by stool consistency and frequency correlates with reduced quality of life determined by *health-related quality of life* (HRQoL) questionnaires in patients with collagenous colitis (45, 48) and lymphocytic colitis (49).

- Activity is defined as  $\geq 3$  stools per day **or**  $\geq 1$  watery stool (BSF 6-7) per day as the mean of seven (six) days.
- Remission is defined as  $< 3$  stools per day **and**  $< 1$  watery stool per day as the mean of seven (six) days.

In conjunction with these definitions, it was recently documented that both stool frequency and consistency correlated with an organic cause of chronic diarrhoea, including BAD, with consistency being the most powerful predictor (47). As there are no validated activity criteria for BAD and chronic diarrhoea is the major symptom, we will apply Hjortswang's criteria for activity and remission.

Diarrhoea remission rates are calculated from comparison of the baseline Study Diary 1 (i.e. Study Day 1 – 7) with the endpoint part of the Study Diary 2 (i.e. Study Day 14 – 20).

### Patient-reported outcomes

#### **Short Health Scale and Short Form 36 version 2**

The Short Health Scale (SHS) is a simple index using four 0 – 100 VAS scales to estimate symptom burden, social function, disease anxiety, and well-being (50). The SHS correlates to the more elaborate HRQoL questionnaires both with the severity of symptoms and global assessment and has been validated in English and in Swedish in patients with both inflammatory and functional bowel disorders (45, 48, 50-53).

The SHS has not been validated in BAD nor in Danish. Therefore, we will compare the result of an SHS questionnaire with the more elaborate SF36v2 and disease activity defined by the Hjortswang criteria.

### **Gastrointestinal Symptom Rating Scale**

The Gastrointestinal Symptom Rating Scale (GSRS) quantifies gastrointestinal symptoms on 15 Likert scales grading symptoms from 1 (mild) to 7 (severe). Added questions specify symptom from the upper and the lower gastrointestinal tract. The GSRS questionnaire is validated in Danish and widely recognised (54).

### **Health-related quality of life and sexual dysfunction**

Sexual dysfunction from chronic diarrhoea due to inflammatory bowel syndrome is common but often the problem goes unnoticed. The questionnaires Female Sexual Distress Scale (FSDS), Female Sexual Function Index (FSFI), and International Index of Erectile Function (IIEF) address the issue in general and the novel IBD-SEX questionnaire address sexual dysfunction from inflammatory bowel disease (IBD) and chronic diarrhoea (55, 56). The IBS-SEX questionnaire is validated in Danish language and validation in Danish patients with IBD is ongoing.

### **Patient-reported “good treatment response”**

A diagnostic therapeutic trial is a common practice instead of testing for BAD. Patients with suspected BAD are treated with a sequestrant and assess the subjective effect. We ask the subjects in the intervention group if they had good response. In order to compare this with the dichotomous Hjortswang response criteria, answers are:

Question: “Do you think that the treatment relieved your diarrhoea?”

a) “No, it was not sufficiently effective”; b) “Yes, it was sufficiently effective”.

In Danish

“Synes du behandlingen fjernede din diarré?”

a) “Nej, den var ikke tilstrækkelig effektiv”; b) “Ja, min diarré forsvandt under behandlingen”.

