## Statistical analysis plan for ancillary endpoints

### Diagnostic validation endpoints

- Placebo-controlled diarrhoea ITT remission rate for colesevelam defined by the Hjortswang criteria in patients with BAD defined by fasting FGF19  $\leq 60$  pg/mL
- ROC analyses to assess the negative predictive values of C4  $< 15$  ng/mL, FGF19  $> 204$  pg/mL, SeHCAT  $> 10\%$ , respectively with diarrhoea remission defined by Hjortswang criteria as gold standard test.
- Repeatability of baseline fasting C4 and FGF19 assessed with marginal limits of agreements (Bland-Altman plot) comparing visit 2 samples with 'optimal' visit 1 samples (ie. fulfilling

visit 2 sampling criteria: fasting, not using statins within a week, no alcohol consumption within 24h)

- Exploratory assessment of the effect of sampling time, statin use, and alcohol intake on C4. This is a regression model of C4 at visit 2 explained by: C4 at visit 1, sampling time, alcohol consumption, statin use, respectively.
- ROC-AUC for all visit 1 C4 samples versus SeHCAT  $\leq 10\%$  as gold standard
- Placebo-controlled subjectively assessed "good response" ITT rate in the primary endpoint population
- Diagnostic values for subjectively assessed "good response" in the colesevelam-arm
  - C4 > 46 ng/mL
  - SeHCAT  $\leq 10\%$

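### The patient-reported 'good response' item means different things in English and Danish, and the two Danish answers are not complementary

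*Combined protocol and SAP*

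**What the plan says.** All references are to the combined protocol and SAP. Under Methods, the section on patient-reported good treatment response explains that a trial of a sequestrant, judged by the patient's own impression, is common practice in place of testing for bile acid diarrhoea. The protocol therefore puts one question with two answers to the subjects and gives it in English and then in Danish.

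- English: the question is "Do you think that the treatment relieved your diarrhoea", with the answers "No, it was not sufficiently effective" and "Yes, it was sufficiently effective".
- Danish: the question is "Synes du behandlingen fjernede din diarré", with the answers "Nej, den var ikke tilstrækkelig effektiv" and "Ja, min diarré forsvandt under behandlingen".

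The two-answer format has a stated reason: "In order to compare this with the dichotomous Hjortswang response criteria, answers are".

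The item is used under Diagnostic validation endpoints, in the analysis plan for ancillary endpoints. One use is a placebo-controlled comparison of subjectively assessed good response, as an "ITT rate in the primary endpoint population". The other is a set of diagnostic values for good response in the colesevelam arm, for C4 > 46 ng/mL and for SeHCAT ≤ 10%.

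**The concern.** The two versions set different thresholds. The English asks for enough relief; the Danish asks for the diarrhoea to have gone. Only the no-answer is carried over literally.

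Two problems follow. First, an English report that quotes the protocol's English item would describe a question that Danish respondents did not see. Second, whatever the English says, the Danish form pairs a yes that means resolution with a no that means insufficient effect, and leaves the ground between them unassigned.

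The item serves as the outcome in one ancillary analysis and as the reference standard in the other. In the second, moving the threshold can change sensitivity, specificity and predictive values. The Background notes that reliance on subjective response has not been validated. That makes it important that this item, which is meant to examine the practice, has one clear meaning.

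**Working it through.** No formula applies to the wording, and the plan states no expected good-response rate to reproduce. The check is a side-by-side reading; the English glosses of the Danish are mine.

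| Element | English text | Danish text | Literal sense of the Danish | Same? |
|---|---|---|---|---|
| Question | "Do you think that the treatment relieved your diarrhoea" | "Synes du behandlingen fjernede din diarré" | Do you think the treatment removed your diarrhoea | No: relief against removal |
| No | "No, it was not sufficiently effective" | "Nej, den var ikke tilstrækkelig effektiv" | No, it was not sufficiently effective | Yes |
| Yes | "Yes, it was sufficiently effective" | "Ja, min diarré forsvandt under behandlingen" | Yes, my diarrhoea disappeared during the treatment | No: enough effect against disappearance |

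**Step 1: are the answers complementary?** Take three kinds of patient.

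- Diarrhoea gone: yes in both languages.
- Effect not enough: no in both languages.
- Effect enough, but diarrhoea still present: yes in English. In Danish, yes is untrue because the diarrhoea did not disappear, and the wording of no is untrue because the effect was enough.

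The English pair covers all three; the Danish pair covers the first two. The third patient may tick no (following the question), tick yes (following the sense of having been helped) or leave the item blank. The documents give neither the share of such patients nor any indication of how they would answer.

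**Step 2: which version do patients see?** No section says so outright. The Inclusion criteria require the ability to consent after written and oral information in Danish, and the protocol supplies Danish wording. It is a reasonable inference, not a stated fact, that the Danish text is the one administered.

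**Step 3: which version suits the stated purpose?** The section on Hjortswang's criteria defines remission as a mean of < 3 stools and < 1 watery stool per day. Disappearance of diarrhoea is arguably closer to that than sufficient effect is. The choice of wording can therefore affect the agreement between the item and diary remission.

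**Step 4: how much does one answer weigh?** This is the weight of a single changed answer, not an estimate of the effect.

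- Good-response rate in the primary endpoint population: the Power calculation plans 23 patients with bile acid diarrhoea per arm, so one answer is 1/23 = 4.3 percentage points of an arm's rate.
- Diagnostic values in the colesevelam arm: 170 patients with diarrhoea allocated 1:1 give 170/2 = 85 in that arm, so one answer is 1/85 = 1.2 percentage points of that arm's overall good-response proportion.

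**Step 5: what depends on the item?** Neither the primary endpoint nor any of the five secondary endpoints uses it. The primary endpoint and the first three secondary endpoints are Hjortswang remission from the diary; the other two are stool counts and the Short Health Scale sum.

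**The case against.** The case for leaving this alone has several parts.

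- **The Danish question itself gives direction.** It asks whether the diarrhoea was removed, so a patient whose diarrhoea persisted can answer no, even though the clause after the no fits badly. This stands in part. It softens the gap but does not close it, because the printed no-answer still asserts insufficient effect.
- **If only the Danish is used, patients get one consistent instrument and the English is merely a gloss.** This stands. Both arms receive the same item, and nothing in the documents shows that the colesevelam–placebo contrast is biased. Misreporting arises only if results are described in the English wording. The protocol does, however, use the good-response label in its own endpoint list.
- **The stakes are low.** This stands. The analyses are ancillary, and Planned publications confines the main paper to primary and secondary endpoints.

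A reader might also infer two stronger points that the documents do not support. One is that the Danish wording would underestimate good response by some definite amount. That assumes every partly relieved patient ticks no, a known share of such patients, and that the English is the intended construct; none of these is in the documents. The other is that the placebo arm is not asked, because the section speaks of the intervention group. The Design section defines the intervention as colesevelam or placebo, and blinding until data lock prevents the question from being put to one arm only. The phrase most naturally means everyone randomised.

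**Conclusion.** The protocol defines one patient-reported outcome in two non-equivalent ways, and the Danish version has answers that do not complement each other. Both facts can be read directly from the text. This is more than a slip of translation, because the outcome feeding two planned analyses has no single definition. It is limited to ancillary results and does not touch the sample size, the primary or secondary endpoints, or the main conclusion.

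The size and direction of any effect cannot be estimated from the documents. The per-answer weights above show only that few changed answers would be visible in the smaller population. The concern about reporting rests on two assumptions: that the Danish text is the one administered, and that results would be reported under the English wording or label. The lack of complementary Danish answers needs only the first.

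**What to change.** **If the Danish form is already in use:** replace the English in the Methods section with a literal translation of the Danish question and both answers. In that section and under Diagnostic validation endpoints, rename the outcome patient-reported disappearance of diarrhoea. This also fits the stated comparison with Hjortswang remission. State how unanswered items are treated, since a blank is one likely response from a partly relieved patient. The cost is a wording correction; no new data are needed.

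**If the form is not yet in use:** choose one construct, either disappearance or sufficient effect. Word the Danish yes and no as exact complements and make the English match. There is a trade-off to record: sufficient effect is less close to Hjortswang remission, so it would suit the stated comparison less well. The cost is a revised item before first use.

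In either case the phrase about the intervention group may be clarified as all randomised subjects. That is a matter of clarity and not a separate error.

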## **Blinding**

**Initial blinding:** Over-encapsulation makes colesevelam and placebo tablets identical. These are produced, packed, and uniquely numbered at the Hospital Pharmacy of the Capital Region, from where packages are distributed to each study centre.

**Maintaining blinding:** Due to the expected treatment effect and possible side effects, maintaining subject blinding could be difficult. This potential bias cannot be avoided.

To avoid investigators to be unblinded, dose titration and AE registration during treatment are performed by an independent study nurse.

We assess subject blinding early in the treatment period and again at treatment end. We assess investigator blinding at treatment end. Each assessment the question is: “Do you think you/the

subject is given a) Colesevelam, b) Don't know, c) Placebo. With this information, we quantify both initial and maintained blinding to estimate the size of potential bias (57-60).

The blinding continues until the last subject has completed the clinical study phase and all data entries have been checked and locked. At this time point, the blinding is unveiled, all subject are informed, and the treatment is documented in the medical chart.

## Emergency unblinding

Sealed envelopes for emergency unblinding are enclosed with each delivery from the Pharmacy to a study centre for the local primary investigator with a copy to the Sponsor. The local investigator or Sponsor may use such an envelope to unblind the treatment at any time and without restrictions if it is deemed necessary. The study subjects are also instructed to keep the contact information for the primary investigator who is contacted in case of any emergency that could warrant unblinding of the study intervention.

In case of unblinding, two dated signatures are needed on the envelope; in an emergency, these need not be from investigator or subinvestigator. Signing the envelope states that it will be opened, and beforehand is intact and untampered.

## Randomisation

A randomisation list is made by the Hospital Pharmacy of the Capital Region by computer randomisation distributing consecutive unique numbers in variable block sizes of two, four, or six to one of the two treatment arms ([www.randomization.com](http://www.randomization.com)). The different block sizes hinder deduction of the allocation of the ultimate slots in a block and secure a 1:1 allocation.

The Hospital Pharmacy of the Capital Region keeps the randomization lists separately and exclusively until study end.

## Biochemistry

All samples are prepared and immediately frozen for later bulk analysis once inclusion is finished. FGF19 is analysed by commercially available ELISA assay (R&D Systems, MN, USA). C4 is analysed with liquid chromatography-tandem mass spectrometry (LC-MS/MS) in the Department de Chimie, Sorbonne Universités, Paris ([name]) (61). C4 will also be analysed in the department of Clinical Biochemistry, Rigshospitalet, Copenhagen ([name]). This founds future clinical availability of the C4 analysis in Denmark. Therefore, we will use the Copenhagen C4 measurements for the endpoint analyses. Ancillary analyses comparing C4 from the two laboratories will be done.

Routine blood samples are analysed in the hospital laboratories of participating centres. These include ALT, ALP, amylase, HDL, LDL and total cholesterol, triglycerides, bilirubin, glucose with sampling time specified elsewhere. In total, these samples comprise 24 mL blood from each

subject. We accept differences in laboratory reference values and procedures in between study centres as these analyses do not comprise endpoints.

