## Aims

1. To determine the efficacy and safety of colestevlam for treating bile acid diarrhoea (BAD).
2. To correlate both the current scintigraphic Selenium conjugated Tauro-homocholic acid retention test (SeHCAT) and the biochemical marker of BAD 7 $\alpha$ -hydroxy-4-cholesten-3-one (C4) with colestevlam treatment response, and to validate the cut-off values determined in the VABAD trial (1).

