## Biochemical tests in our population – choice of C4 cutoff

We studied FGF19 after stimulation with a mixed meal (30) and then with combinations of the meal plus chenodeoxycholic acid (31) and pilot results were promising. Based on these preliminary results, we did a prospective validation study (VABAD) of 71 consecutive diarrhoea patients referred for SeHCAT. We found that neither stimulated nor fasting FGF19 were better than C4. The fasting FGF19 receiver operating characteristics (ROC) analysis versus SeHCAT ≤ 10% showed an area under the curve (AUC) of 0.73 and for C4 it was 0.83. Thus, C4 is the better biochemical test. Of the 71 VABAD patients, 59 fulfilled the Hjortswang criteria for diarrhoea (described below) that is a prerequisite in SINBAD. Table 1 shows ROC results for this subpopulation. The C4 cut-off value of 46 ng/mL had optimal combined diagnostic characteristics with a diagnostic accuracy of 74%. 13 (22%) of the 59 patients had C4 > 46 ng/mL. The cut-off > 58 had higher PPV, and 11 of 59 (19%) had C4 > 58ng/mL. We chose the 46 ng/mL cutoff for the primary endpoint to keep false negative test results at a minimum.

TABLE 1 Results from the VABAD study	SeHCAT≤10% N=25 Median (IQR)	SeHCAT>10% N=34 Median (IQR)	ROC analysis, AUC (95% CI)	Cutoff for positive test	Sens./spec. (%)	PPV/NPV (%)
Fasting C4	47 (21–71)**	11 (9–23)	0.82 (0.71–0.93)**	C4 > 25	72 / 82	64 / 80
				C4 > 46	52 / 91	72 / 74
				C4 > 58	44 / 94	77 / 70
Fasting FGF19	75 (57–146)*	115 (8–220)	0.69 (0.54–0.83)*	FGF19 ≤ 85	60 / 77	65 / 72
FGF19 in pg/mL and C4 in ng/mL. The statistical significance of the ROC curves was tested nonparametric versus true area=0.50. *p=.02; **p=.00003						

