## Endpoints

### Primary endpoint

Placebo-controlled ITT diarrhoea remission rate defined by the Hjortswang criteria for colesevelam in patients with BAD defined by  $C4 > 46$  ng/mL.

**Handling of missing data:** drop-outs are set as treatment failures in the ITT analysis if less than five of the last seven treatment days that comprise the endpoint assessment period are complete. If five or more of these days are complete, a mean of these days will be used for calculating the Hjortswang response criterium.

**Statistical analysis:** data will be longitudinally correlated (baseline, run-in, endpoint assessment period for each patient) and nested within study sites. Thus, data will not be independent and cannot correctly be assessed with simple statistical tests. Therefore, we will fit an appropriate generalized linear mixed-effects model with an unstructured covariance pattern of the chance of response with colesevelam versus placebo. In addition, baseline adjustments for the severity of

diarrhoea (mean per day sum of Bristol type 6 and 7 stools) and the severity of bile acid malabsorption (visit 2 C4 value) will be made to avoid skewed randomisation of these prognostic covariates by chance (40). This baseline adjustment is clinically relevant as, in the future, diarrhoea severity and C4 should be available for physicians before starting therapy.

The model fit will be assessed by inspection of scaled residual plots and QQ-plots.

**Sensitivity analyses:** The robustness of the statistical modelling of the primary endpoint will be addressed in sensitivity analyses of different approaches.

Different handling of missing values: 1) any missing diary day of the last seven treatment days and the patient treatment is set to failure; 2) excluding patients who drop out due to large pill size (the DB caps used for trial blinding are significantly larger than the colesevelam tablet), 3) using multiple imputations for missing values.

Strict Hjortswang's response criteria: no watery stools (Bristol stool type 6 or 7) during the last seven treatment days.

Different C4 cut-off used to define bile acid diarrhoea: C4 > 25 ng/mL; C4 > 58 ng/mL.

If possible, given that the study is not powered for stratification, we will assess remission rates in stratification intervals defined by C4 0–25 ng/mL, >25–46 ng/mL.

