## Elucidation of further aspects of treatment effect

- Placebo-controlled ITT diarrhoea remission rate defined by the Hjortswang criteria for colesevelam in patients with BAD by C4  $\geq 46$  ng/mL AND
  - fecal primary bile acids >10%, and >15%
- Logistic regression model predicting remission in the colesevelam group for
  - C4 controlled for baseline mean stools/day
    - Sensitivity, specificity, PPV and NPV for C4 > 46 ng/mL
      - Model characteristics reported with mean stools/day
  - SeHCAT controlled for baseline mean stools/day
    - Sensitivity, specificity, PPV and NPV for SeHCAT  $\leq 10\%$

- Six-month follow up on the aetiology of diarrhoea
- Six -month follow up on medication
- Exploratory regression analyses to determine if fecal or plasma bile acid profile may be a predictor for diagnosis and for treatment response.
- Placebo-controlled change in fecal bile acids during treatment with colesevelam.

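### Does applying the VABAD cut-off of 46 ng/mL to Copenhagen C4, with no Paris-based sensitivity analysis, weaken the primary analysis?

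*Combined protocol and SAP*

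**What the plan says.** The section on the choice of C4 cut-off takes 25, 46 and 58 ng/mL from 59 VABAD patients with diarrhoea, and explains the choice among them: "We chose the 46 ng/mL cutoff for the primary endpoint to keep false negative test results at a minimum". The second aim includes the intention "to validate the cut-off values determined in the VABAD trial".

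Under Biochemistry, C4 is measured by LC-MS/MS in Paris and also at a Copenhagen hospital laboratory. The reason given for the second laboratory is future clinical availability in Denmark. The plan then states "Therefore, we will use the Copenhagen C4 measurements for the endpoint analyses" and "Ancillary analyses comparing C4 from the two laboratories will be done". For routine blood samples, the same section says "We accept differences in laboratory reference values and procedures in between study centres as these analyses do not comprise endpoints".

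Among the sensitivity analyses of the primary endpoint is "Different C4 cut-off used to define bile acid diarrhoea: C4 > 25 ng/mL; C4 > 58 ng/mL". If feasible, remission is also to be examined in the C4 bands 0–25 and above 25 to 46. None of the listed analyses changes the laboratory.

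**The concern.** A fixed concentration threshold carries over from one assay to another only if the two assays read alike. The plan takes its threshold from one study, applies it to a named laboratory, and describes no calibration between the two. Its tolerance of laboratory differences for routine samples rests on those samples not being endpoints. C4 does define the primary population and is also a covariate in the primary model, so that reasoning does not excuse a C4 difference.

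At stake are who enters the primary analysis, how many they are, and what a validated 46 means. The ancillary output "Sensitivity, specificity, PPV and NPV for C4 > 46 ng/mL", which concerns prediction of remission in the colesevelam arm, would describe the Copenhagen threshold. If it looked poor, a reader might ask whether the cut-off failed or the assay differed.

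**Working it through.** **Reproducing the plan's size.** Inputs from the Power calculation section: remission 67% and 27%, two-sided alpha 0.05, 80% power, 1:1 allocation. With the pooled z-test and a mean proportion of 0.47:

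n per arm = [1.960 × √(2 × 0.47 × 0.53) + 0.842 × √(0.67 × 0.33 + 0.27 × 0.73)]² / 0.40² = 23.2.

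Power at 23 per arm is 79.6%, and 46/0.27 = 170. Both of the plan's figures reproduce.

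**Counts above each cut-off.** From the sensitivities and specificities in Table 1 (25 patients with SeHCAT ≤10%, 34 with >10%):
- above 25: 18 + 6 = 24 of 59
- above 46: 13 + 3 = 16 of 59 (27%, the figure used in the Power calculation; the 13 (22%) in the background text equals the true positives alone)
- above 58: 11 + 2 = 13 of 59

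**Effect of a laboratory difference.** Let r be the Copenhagen reading divided by the VABAD-scale reading. The documents give no value, so every r below is an assumption. Copenhagen C4 above 46 then selects VABAD-scale C4 above 46/r. Counts are interpolated linearly in ln(C4) and multiplied by 170/59. Power uses half the patients per arm and assumes that any added patients respond like the rest.

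| r | 46/r | Count of 59 | Of 170 | Power | Copenhagen value equal to VABAD 46 (46 × r) | VABAD value at Copenhagen 58 | VABAD value at Copenhagen 25 |
|---|---|---|---|---|---|---|---|
| 0.8 | 57.5 | 13.11 | 37.8 | 70.9% | 36.8 | 72.5 | 31.3 |
| 0.9 | 51.1 | 14.64 | 42.2 | 75.8% | 41.4 | 64.4 | 27.8 |
| 1.0 | 46.0 | 16.00 | 46.1 | 79.7% | 46.0 | 58.0 | 25.0 |
| 1.1 | 41.8 | 17.25 | 49.7 | 82.7% | 50.6 | 52.7 | 22.7 |
| 1.2 | 38.3 | 18.39 | 53.0 | 85.2% | 55.2 | 48.3 | 20.8 |

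If the added patients gain nothing from colesevelam (27% in both arms), the colesevelam rate at r = 1.2 is (16 × 0.67 + 2.39 × 0.27)/18.39 = 61.8% and power is 73.5%. At r = 1.1 the figures are 64.1% and 76.4%.

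**Comparison with existing uncertainty.** The Wilson 95% interval for 16/59 is about 17.4% to 39.6%, or 30 to 67 of 170. That is wider than the 38 to 53 produced by an assumed 20% laboratory difference in either direction.

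**Bias.** C4 is taken fasting at visit 2, before treatment. Samples are frozen and analysed in bulk after inclusion ends, and randomisation does not use C4. A laboratory shift therefore acts on both arms alike. A proportional shift only rescales the C4 covariate.

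**What the planned cut-offs cover.** The alternative cut-offs are applied to Copenhagen values. The analysis above 58 recovers VABAD 46 when r = 58/46 = 1.26, so it lies close to the case of a 20% high reading. The analysis above 25 recovers it when r = 25/46 = 0.54, a reading 46% low. A moderately low reading is the less well covered case. At r = 0.8, however, the patients lost from the primary population have Copenhagen values from 36.8 to 46. They all fall in the planned band above 25 to 46 and are included in the analysis above 25.

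**What does not depend on the C4 laboratory.** The secondary endpoints defined by SeHCAT ≤10% (with ≤5% and ≤15% as sensitivity analyses for the ITT version) and the stool outcomes in all treated patients do not select on C4. The ancillary ROC area for C4 against SeHCAT does not change under a proportional shift.

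**The case for a change.** The best case for a change is that it costs little. Paris C4 is already to be measured, so repeating the primary model with Paris C4 above 46 needs a sentence in the plan and one more run. Fixing the comparison method before unblinding would remove any appearance of choosing a laboratory after seeing results. With about 80% power and 46 patients, moving four to eight across the line is not trivial. The planned cut-offs mimic a uniform shift but cannot show patient-by-patient disagreement between the laboratories, and the SeHCAT endpoints cannot validate a C4 threshold.

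All of that is fair, and it shows that the rerun would be reasonable. It does not show that the plan is wrong. The risk of a post hoc laboratory choice is already closed, because Copenhagen is named in advance. What the rerun would tell us depends on where VABAD C4 was measured, which the available text does not say; the pages listing the cooperating departments are not in it. If VABAD used Paris, the planned laboratory comparison would already reveal a difference. If it used Copenhagen, there is no transfer problem. If it used a third assay, neither laboratory restores the VABAD scale.

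**Conclusion.** No change follows. It is correct that the laboratory comparison is ancillary and that no primary sensitivity analysis uses Paris C4. Using one prespecified laboratory, the one intended for future Danish practice, is a fair trade-off: the trial tests the threshold on the assay that clinicians there would use. The randomised comparison stays unbiased, and the two-laboratory comparison that would help interpret a disappointing cut-off is already planned. Its method is not described, but this is a gap that analysts can fill sensibly.

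The possible size is about 38 to 53 patients above 46 instead of 46, with power of about 71% to 85%. This rests on an assumed proportional difference of up to 20%, on interpolation from small VABAD counts, and on VABAD having used an assay other than Copenhagen's, which is not established. The effect on sensitivity and specificity for remission cannot be sized from the documents. A supplementary run with Paris C4 and a note naming the VABAD assay in the report would be useful, but the plan does not depend on either.
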